## **17.6 Analysis of secondary endpoints**

### **17.6.1 Adverse events**

An overview of all AEs, including SAEs, intensity, relationship to IMP, and deaths will be presented by SOC and PT.

Incidence of AEs and SAEs will be summarised by SOC and PT.

All AE data will be listed subject and include the verbatim term entered by the Investigator.

### **17.6.2 Physical examination**

Clinically significant and non-clinically significant abnormal findings will be specified and presented by subject and summarised.

Changes over time will be presented using shift tables, if considered applicable.

All data will be listed by subject.

### **17.6.3 Vital signs**

Vital signs (systolic/diastolic BP, pulse) will be summarised. Data will be presented with absolute and percent change from baseline at each visit. Clinical evaluation of vital signs will be summarised in frequency tables.

All data will be listed by subject.

### **17.6.4 Body temperature**

Body temperature will be summarised. Data will be presented with absolute and percent change from baseline at each visit.

All data will be listed by subject.

### **17.6.5 Resting 12-lead ECG**

All ECGs will be categorised as "normal", "abnormal, not clinically significant", or "abnormal, clinically significant" (as judged by the Investigator) and summarised using frequency tables.

Changes over time will be presented using shift tables, if considered applicable.

All data will be listed by subject.

#### 17.6.6 *Laboratory safety assessments*

Safety laboratory data will be summarised with absolute and percent change from baseline at each visit.

Abnormal, clinically significant values will be summarised separately if considered appropriate.

All data will be listed by subject.

2 VERSION HISTORY

This statistical analysis plan for study GS-1002 is based on the protocol dated 29JAN2020.

Table 1 SAP Version History Summary

SAP version	Approval Date	Changes	Rationale
0.1	15MAY2020	-	Version for internal review
0.2	20MAY2020	Minor adjustments	Version for Sponsor review
0.3	02JUN2020	Minor adjustments	Version for Sponsor review
1	04JUN2020	NA	Original version

STATISTICAL ANALYSIS PLAN

Protocol Version No: Final v 1.0; 29JAN2020

Study Code: GS-1002

CTC Project No: [contact]

CLINICAL TRIAL CONSULTANTS AB

3 INTRODUCTION

This statistical analysis plan gives details regarding the statistical analyses and data presentation outlined in the final clinical study protocol (CSP) for the study *GS-1002*. Any changes from the final CSP are given in Section 9.

4 CLINICAL STUDY DETAILS

4.1 Clinical study objectives and endpoints

Table 2 – Study objectives and endpoints

Objects	Estimands/Endpoints
Primary	

1. To evaluate the pharmacokinetics (PK) of two different solid formulations of oral GS-248 in healthy subjects.
 
2. To evaluate the effect of food on the PK of one of the two formulations of GS-248.
	
1.1 The PK parameters of a single dose of two different formulations of GS-248 in fasting conditions. The PK parameters to be assessed include, but are not limited to, maximum plasma concentration (C_{max}), time to C_{max} (T_{max}), area under the plasma concentration versus time curve (AUC) from timepoint 0 to the last measured timepoint (AUC_{0-last}), AUC from timepoint 0 to infinity (AUC_{0-inf}), plasma half-life associated with the terminal elimination phase ($T_{1/2(z)}$), volume of distribution associated with the terminal elimination phase following non-intravenous administration (V_z/F), and total clearance of the drug from plasma following non-intravenous administration (CL/F).
 
2.1 The relative bioavailability of GS-248 after a single dose of Formulation A versus Formulation B, and of one of the two formulations in fed versus fasting conditions.
 
2.2 The PK parameters of a single dose of one of the two formulations of GS-248 in fed conditions.

Secondary	

1a. To evaluate the safety and tolerability of two different solid formulations of oral GS-248 in healthy subjects.
 
1b. To evaluate the safety and tolerability of one of the two formulations of oral GS-248 given after a standardised high-fat high-calorie breakfast.
	
Applicable for both objectives
 
1.1 Frequency, intensity, and seriousness of adverse events (AEs).
 
1.2 Clinically significant changes in: - Physical examination - Vital signs - Body temperature - Resting 12-lead electrocardiogram (ECG) - Safety laboratory parameters

Tertiary/Exploratory	
NA	NA

4.2 Clinical study design

This was a Phase I, open, one-sequence, three-period study in healthy volunteers to evaluate the PK, safety and tolerability of two different solid formulation of GS-248, as well as the effect of a high-calorie high-fat breakfast on the PK and safety of one of these two formulations.

4.3 Statistical hypotheses

No formal hypothesis was defined in the protocol. However, p-values will be calculated as outlined in this SAP, based on the null hypothesis that there is no difference in systemic exposure with either different formulations or fed/fasting states.

4.4 Number of subjects

A total of 14 subjects were included in the study.

4.5 Randomisation

Not applicable.

4.6 Blinding

This was an open study and thus no blinding was needed.

5 STATISTICAL AND ANALYTICAL PLANS

5.1 Sample size determination

No formal sample size calculation was performed for this study. The proposed sample size was considered sufficient to provide adequate information for the study objectives.

14 subjects were dosed to achieve a total of at least 12 evaluable subjects that completed the study. Subjects were evaluated for safety analysis after receiving one dose of the study drug.

5.2 Definition of analysis sets

5.2.1 Safety analysis set

The safety analysis set will consist of all subjects who received at least one dose of the investigational medical product (IMP).

5.2.2 Pharmacokinetics analysis set (PKAS) - formulation

The PKAS formulation will consist of all subjects who received a single dose of both Formulation A and Formulation B, from whom PK blood samples were collected after IMP dosing, and for whom there were no AEs or protocol deviations judged to affect the analysis of the data.

5.2.3 PKAS – food interaction set

The PKAS food interaction set will consist of all subjects who received all three IMP doses, from whom PK blood samples were collected after IMP dosing, and for whom there were no AEs or protocol deviations judged to affect the analysis of the data.

5.2.4 Use of analysis set

The safety analysis set population will be used for the safety evaluation and the PKAS will only be used for the PK evaluations.

If any of the analysis populations are identical, only one will be used.

5.3 Definition of baseline

Baseline measurement will be defined as the latest measurement prior to first dose of the IMP.

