#### **Duration of treatment**

Subjects will receive in total 3 single doses of GS-248, with a wash-out period of at least 4 days in between each IMP administration.

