### 17.1 General

Continuous data will be presented in terms of evaluable and missing observations, arithmetic mean, standard deviation (SD), median, minimum and maximum value. In addition, for the parameters AUC and  $C_{max}$  the geometric mean and coefficient of variation (CV) will be presented.

Categorical data will be presented as counts and percentages. When applicable, summary data will be presented by treatment, and by assessment time. Individual subject data will be listed by subject number, treatment, and, where applicable, by assessment time.

All descriptive summaries and statistical analyses will be performed using SAS Version 9.4 or later (SAS Institute, Inc., Cary, NC).

Baseline will be defined as the last data collection point prior to each administration of IMP.

All hypothesis testing will use a significance level of 5%.

No imputation of missing data will be performed.

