8.4.1.3 Vital signs

This section refers to secondary objective #1 and endpoint 1.2.

Vital signs (systolic/diastolic BP, pulse) and body temperature will be summarised. Data will be presented with absolute and percent change from baseline at each visit. Clinical evaluation of vital signs will be summarised in frequency tables.

All data will be listed by subject. See tables and listings in the statistical output layout, section 14.

8.4.1.4 *ECG resting 12-lead*

This section refers to secondary objective #1 and endpoint 1.2.

All ECGs will be categorised as “normal”, “abnormal, not clinically significant”, or “abnormal, clinically significant” (as judged by the investigator) and summarised using frequency tables. Changes over time will be presented using shift tables, if considered applicable.

All data will be listed by subject. See tables and listings in the statistical output layout, section 14.

8.4.1.5 *Safety laboratory analyses*

This section refers to secondary objective #1 and endpoint 1.2.

Safety laboratory data will be summarised with absolute and percent change from baseline at each visit. Abnormal, clinically significant values will be summarised separately if considered appropriate.

All data will be listed by subject. See tables and listings in the statistical output layout, section 14.

8.5 **Sensitivity analysis**

No sensitivity analyses are planned to be performed.

8.6 **Supplementary analyses**

No supplementary analyses are planned to be performed.

8.7 **Tertiary/exploratory endpoint(s) analysis**

Not applicable.

8.8 **Discontinuation**

Patients who discontinue from IMP treatment will be tabulated. The reason for discontinuation will be given. For discontinuation due to AE, the AEs will be given.

8.9 **Other analyses**

Not applicable.

8.10 **Interim analysis**

Not applicable.

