9 CHANGES FROM THE CSP

10 STATISTICAL DELIVERABLES

The following documents will be delivered:

- SAP
- Statistical analyses and summary tables

STATISTICAL ANALYSIS PLAN

Protocol Version No: Final v 1.0; 29JAN2020

Study Code: GS-1002

CTC Project No: [contact]

CLINICAL TRIAL CONSULTANTS AB

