13.2 Appendix 2 – changes to protocol-planned analyses

14 STATISTICAL OUTPUT LAYOUT

14.1 Tables

Table 14.1.1 Baseline characteristics and demographics (analysis set)

	Total (N=X)
Age (years)	n/nmiss x/x
Mean (SD)	x.x (x.x)
Median (Min, Max)	x.x (x.x)
Body Mass Index (kg/m2)	n/nmiss x/x
Mean (SD)	x.xx (x.xx)
Median (Min, Max)	x.xx (x.x, x.x)
Height (cm)	n/nmiss x/x
Mean (SD)	x.x (x.x)
Median (Min, Max)	x.x (x.x)
Weight (kg)	n/nmiss x/x
Mean (SD)	x.xx (x.xx)
Median (Min, Max)	x.xx (x.x,x.x)
Sex	Female Male
	x (x.x%) x (x.x%)
Ethnicity	Hispanic Or Latino Not Hispanic Or Latino
	x (x.x%) x (x.x%)
Race	American Indian Or Alaska Native Asian
	x (x.x%) x (x.x%)

STATISTICAL ANALYSIS PLAN

Protocol Version No: Final v 1.0: 29JAN2020

CTC Project No: [contact]

Total (N=X)	
Black or African American	x (x.x%)
Native Hawaiian or other Pacific Islander	x (x.x%)
White	x (x.x%)

[STUDYID] Summarised demographics data.
Data based on the [analysis set].
SAS program: summary_demographics.sas. Run by: [USERNAME], [USER_EMAIL] [TIMESTAMP]

STATISTICAL ANALYSIS PLAN

Protocol Version No: Final v 1.0; 29JAN2020

CTC Project No: [contact]

CLINICAL TRIAL CONSULTANTS AB Study Code: GS-1002

Table 14.1.2 Subject disposition (all subject)

	Total
Screened subjects	x
Withdrawn prior to [dose]	x
--- Withdrawal reason x	x
--- Withdrawal reason x	x
--- Withdrawal reason x	x
Included subjects	x
--- [Formulation A]	x
--- [Formulation B]	x
--- [Formulation A/B fed]	x
Withdrawn subjects	x
--- Withdrawal reason x	x
--- Withdrawal reason x	x
--- Withdrawal reason x	x
Completed subjects	x
--- [Formulation A]	x
--- [Formulation B]	x
--- [Formulation A/B fed]	x
Included in [Safety analysis set]	x
Included in [PK analysis set (fed)]	x
Included in [PK analysis set (food interaction)]	x
Subjects at [VISIT 1]	x

GS-1002_SAP_v1.0_04JUN2020

CONFIDENTIAL

STATISTICAL ANALYSIS PLAN

Protocol Version No: Final v 1.0: 29JAN2020

CTC Project No: [contact]

	Total
Subjects at [VISIT 2]	x
Subjects at [VISIT 3]	x
Subjects at [VISIT 4]	x
Subjects at [VISIT 5]	x
Subjects at [VISIT 6]	x
Subjects at [VISIT 7]	x

[STUDYID] disposition, SAS program: disposition.sas. Run by: [USERNAME], [USER EMAIL] [TIMESTAMP]

Table 14.1.3. Medical history events by system organ class and preferred term (analysis set)

System organ class Preferred term	Total N=X	m
	n(%)	
Total	X(X.X%)	X
SOC 1	X(X.X%)	X
SOC 1 PT 1	X(X.X%)	X
SOC 1 PT 2	X(X.X%)	X
SOC 1 PT 3	X(X.X%)	X
SOC 2	X(X.X%)	X
SOC 2 PT 1	X(X.X%)	X
SOC 2 PT 2	X(X.X%)	X

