Assessment	Assessment timepoint	Result	Formulation A/B		
			Formulation A	Formulation B	Formulation A/B
[Parameter 1]	[Assessment timepoint 1]	[RESULT 1]	x(x.x%)/X	x(x.x%)/X	x(x.x%)/X
		[RESULT 2]	x(x.x%)/X	x(x.x%)/X	x(x.x%)/X
	[Assessment timepoint 2]	[RESULT 1]	x(x.x%)/X	x(x.x%)/X	x(x.x%)/X
		[RESULT 2]	x(x.x%)/X	x(x.x%)/X	x(x.x%)/X

Data based on [ANALYSIS SET].
 [STUDYID] [DOMAIN]: [PARAMETER CATEGORY], SAS program: descriptive_stat_tables.sas. Run by: [USERNAME], [USER EMAIL] [TIMESTAMP]

Table 14.3.x.x. ECG – shift table (analysis set)

Assessment	Assessment timepoint	Result	NORMAL	ABNORMAL CS	ABNORMAL NCS	MISSING	TOTAL
			n (%)	n (%)	n (%)	n (%)	n (%)
[Parameter 1]	[Assessment timepoint 1]	NORMAL	X (X%)	X (X%)	X (X%)	X (X%)	X (X%)
		ABNORMAL CS	X (X%)	X (X%)	X (X%)	X (X%)	X (X%)
		ABNORMAL NCS	X (X%)	X (X%)	X (X%)	X (X%)	X (X%)
		MISSING	X (X%)	X (X%)	X (X%)	X (X%)	X (X%)
		TOTAL	X (X%)	X (X%)	X (X%)	X (X%)	X (X%)

Data based on [ANALYSIS SET].
 [STUDYID] [DOMAIN]: [PARAMETER CATEGORY], SAS program: descriptive_stat_tables.sas. Run by: [USERNAME], [USER EMAIL] [TIMESTAMP]

Table 14.3.x.x. Safety laboratory results (analysis set)

[Parameter 1] (unit)	Result Category	Assessment timepoint	Formulation A/B		
			Formulation A	Formulation B	Formulation A/B fed
[Assessment timepoint 1]	Measured value	n	x	x	x
		Mean (SD)	x.xxx (x.xxx)	x.xxx (x.xxx)	x.xxx (x.xxx)
		Median (Min, Max)	x.xxx (x.xx, x.xx)	x.xxx (x.xx, x.xx)	x.xxx (x.xx, x.xx)
[Assessment timepoint 2]	Measured value	n	x	x	x
		Mean (SD)	x.xxx (x.xxx)	x.xxx (x.xxx)	x.xxx (x.xxx)
		Median (Min, Max)	x.xxx (x.xxx, x.xxx)	x.xxx (x.xx, x.xx)	x.xxx (x.xx, x.xx)
Absolute change from baseline	[Assessment timepoint 2]	n	x	x	x
		Mean (SD)	x.xxx (x.xxx)	x.xxx (x.xxx)	x.xxx (x.xxx)
		Median (Min, Max)	x.xxx (x.xxx, x.xxx)	x.xxx (x.xx, x.xx)	x.xxx (x.xx, x.xx)
Relative change from baseline (%)	[Assessment timepoint 2]	n	x	x	x
		Mean (SD)	x.x (x.x)	x.xxx (x.xxx)	x.xxx (x.xxx)
		Median (Min, Max)	x.x (x, x)	x.xxx (x.xx, x.xx)	x.xxx (x.xx, x.xx)

Data based on [ANALYSIS SET].
 [STUDYID] [DOMAIN]: [PARAMETER CATEGORY], SAS program: descriptive_stat_tables.sas. Run by: [USERNAME], [USER EMAIL] [TIMESTAMP]

Clinical chemistry, haematology, coagulation, and urinalysis

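### SAP 5.3 replaces the protocol's baseline before each dose with one baseline before the first dose, undeclared, so shifts that persist between periods enter the Formulation B and fed-dose change columns

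*SAP*

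**What the plan says.** Protocol 17.1 (General) gives a baseline for every dose: "Baseline will be defined as the last data collection point prior to each administration of IMP". SAP 5.3 gives one per subject: "Baseline measurement will be defined as the latest measurement prior to first dose of the IMP". Each subject receives three single doses, "with a wash-out period of at least 4 days in between each IMP administration" (protocol synopsis, Duration of treatment), in the fixed order Formulation A fasted, Formulation B fasted, selected formulation fed.

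Baseline feeds the safety tables. For vital signs and body temperature, SAP 8.4.1.3 says: "Data will be presented with absolute and percent change from baseline at each visit". SAP 8.4.1.5 says the same in substance for laboratory data. The table shells in SAP 14.1 for vital signs, ECG and laboratory results carry rows such as "Absolute change from baseline" under separate columns for A, B and the fed dose. The ECG shift table, if produced, also needs a baseline.

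On departures from the protocol, SAP Section 3 says: "Any changes from the final CSP are given in Section 9". That section ("9 CHANGES FROM THE CSP") is a heading followed directly by Section 10. Appendix 2 ("changes to protocol-planned analyses") is likewise a heading with no entry. Neither is marked as redacted.

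**The concern.** The two documents define the same quantity differently, and the SAP gives no sign that this was intended. SAP 4.4 and 5.1 already describe inclusion and dosing in the past tense, and the study is open, so a changed definition ought to be declared and justified.

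The secondary objectives ask about the safety of each formulation and of the fed dose. A by-treatment change column is read as what happened after that treatment. With one baseline before the first dose, a change that arose earlier and persisted appears again under the next treatment, and a shift in the opposite direction can cancel a new change within the period. Every subject follows the same order, so a time trend cannot be separated from a treatment difference in these columns. The Day -1 values at Visits 4 and 6 precede that period's dose, yet the SAP rule makes them post-baseline values.

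**Working it through.** No figure in the plan depends on the baseline definition, so there is none to reproduce. The check is an identity, a count of affected cells, and a look at what could make the two rules differ.

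**Identity.** Let pre-A, pre-B and pre-F be the Day -1 values before the three doses, and post-B and post-F later values in those periods.

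- Protocol rule: change for B = post-B − pre-B.
- SAP rule: change for B = post-B − pre-A = (post-B − pre-B) + (pre-B − pre-A).
- SAP rule: change for fed = (post-F − pre-F) + (pre-F − pre-A).

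The rules agree for Formulation A and wherever the second bracket is zero. A steady drift of d per period appears as 0, d, 2d across A, B and fed under the SAP rule, and as 0, 0, 0 under the protocol rule.

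**Illustration with assumed values.** Pre-A is 20, the rise after A is 10, and neither B nor the fed dose has any effect.

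| Share of rise left before B | B column, SAP rule | B column, protocol rule |
|---|---|---|
| 0% | 0 | 0 |
| 25% | +2.5 (12.5%) | 0 |
| 50% | +5 (25%) | 0 |
| 100% | +10 (50%) | 0 |

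If B also raises the value by 10 and half of A's rise remains, pre-B is 25 and post-B is 35. The SAP rule gives 35 − 20 = +15 (75%); the protocol rule gives 35 − 25 = +10 (40%).

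**Cells affected (protocol Table 8.1-2).** Vital signs, temperature and ECG have 4 post-dose times per period (2, 8, 24 and 48 h); laboratory tests have 1 (48 h). The baseline differs in two of the three periods:

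- vital signs, temperature, ECG: 2 × 4 = 8 of 3 × 4 = 12;
- laboratory: 2 × 1 = 2 of 3 × 1 = 3.

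**Age of the SAP baseline (minimums).** It is taken on Day -1, one day before the first dose.

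- At the Formulation B dose: 4 + 1 = 5 days.
- At the fed dose: 4 + 4 + 1 = 9 days on the 4-day minimum (synopsis; protocol 8.2), or 4 + 14 + 1 = 19 days on the intervals in Table 8.1-1.
- Under the protocol rule: about 1 day at every dose.

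**What could produce a shift.** Residual drug is not the main route. At the half-life of about 10 h in protocol 6.1.6, the fraction left after 4 days is 0.5^(96/10) = 0.0013, or 0.13%. The shift would have to come from an effect that outlasts the drug or from drift. Two features of the protocol bear on this:

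- Section 9.8.3 lets certain subjects with raised ALT continue under weekly monitoring, so an elevation still present at a later dose is foreseen.
- PK sampling takes 14 samples (pre-dose plus 13) × about 4 mL = 56 mL before the Formulation B baseline and 2 × 56 = 112 mL before the fed baseline. Haemoglobin and haematocrit are safety parameters. The documents do not say that this volume moves them, so this is a possible route, not an established one.

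**The case against.** The strongest reply is that little depends on these rows. The secondary endpoints are adverse events and clinically significant changes, the latter judged by the investigator without reference to the statistical baseline. Measured values are tabulated by time and treatment and all data are listed, so a within-period change can be reconstructed. No test or decision rule uses the change rows. This stands, and it limits how serious the point is. It does not make the summary tables match the protocol.

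Second, no document reports an effect of a single 120 mg dose that outlasts the wash-out, and the single-dose part of the first-in-human study had no noteworthy safety findings. That also stands: the double counting is conditional, and the 8 of 12 and 2 of 3 figures count cells where the baseline differs. They do not measure bias.

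Third, the laboratory shell shows change rows only at its second timepoint, which would fit a baseline specific to each column. The shell is a placeholder and cannot override the explicit sentence in SAP 5.3. Nor can the first dose be read as the first of each period, since each period has only one.

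Fourth, a period-specific baseline can absorb a lasting effect of Formulation A into B's baseline and hide it. That is a fair reason to show both changes, but not to switch definitions without saying so. ECG change from baseline appears only in a shell, and its shift table only if considered applicable, so the ECG part is less certain than the rest.

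**Conclusion.** The point holds and should be fixed. SAP 5.3 contradicts protocol 17.1, and the supplied text declares no change. Followed as written, it adds the between-period shift to every Formulation B and fed-dose change where that shift is not zero.

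The consequence is confined to descriptive secondary safety tables. The primary PK analysis, adverse event counts, clinical-significance judgements, withdrawal criteria, measured-value rows and listings do not change. How far the reported changes would move cannot be derived from the documents.

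The conclusion assumes that Section 9 and Appendix 2 of the SAP are empty in the source and did not lose text in extraction, and that SAP 5.3 is applied in its plain sense.

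**What to change.** Reword SAP 5.3 so that baseline is the last measurement before each IMP administration, specific to the period, as in protocol 17.1. Apply it to every change-from-baseline and shift table, using the Day -1 values of Visits 2, 4 and 6. Keep change from the value before the first dose as an additional display, so that persistent or cumulative shifts remain visible.

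If the sponsor prefers the first-dose baseline as the main one, declare and justify it in SAP Section 9 and present the period-specific change beside it.

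The cost is one SAP sentence and the derivation code, plus the extra display. No new data are needed: Table 8.1-2 already schedules laboratory tests, vital signs, temperature and ECG on Day -1 of each dosing visit.

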5.4 Summary statistics

In general, all data collected will be presented with summary statistics and given in subject data listings. Summary statistics will include at least the number of subjects, mean, standard deviation, median, minimum, and maximum for continuous data. Summary statistics for categorical data will consist of at least frequency and percentage. Tables with summary statistics will be divided by treatment group and assessment time, where applicable. Subject data listings will be sorted by treatment, subject, and timing of assessments.

5.5 Significance level

See section 8.1.

5.6 Multiple comparisons/multiplicity

No adjustment for multiple comparison/multiplicity will be performed. All significant findings must be reviewed for medical relevance.

5.7 Handling of dropouts, missing data, and outliers

Outliers will be included in summary tables and listings and will not be handled separately in any analyses. No imputation of data will be performed.

